#### **10.4.1.3 Additional Dose Levels**

Repeat of any cohort or the addition of interim dose levels (lower than those planned) may be added, as determined by the SRC, depending on the safety results from the prior cohort(s).

Dosing will not exceed 4.0 mcg/kg without a protocol amendment.

Additional cohorts (up to 6 subjects per cohort) may be enrolled as determined by the SRC, to repeat a dose level or to study an interim dose level (lower than those planned) in a new cohort of subjects.

The IRB should be immediately notified of this revised approach.

#### **10.4.1.4 Dose Escalation and Stopping Rules**

Dose escalation to the next dose level (i.e., next cohort) will not take place until after the PI has reviewed the safety data. If any findings in the safety data are of concern, then the SRC comprised of but not limited to, the Sponsor, medical monitor, and the PI will convene to determine if adequate safety and tolerability from the previous cohort has been demonstrated to permit proceeding to the next cohort. The SRC review of all pertinent blinded safety/tolerability data must comprise of physical examinations, ECGs, vital signs, clinical laboratory tests [including coagulation], thrombin time, injection site reaction, and AEs available for all subjects who have completed up to Day 14 procedures.

Data from all subjects in the cohort will be used and reviewed for a dose escalation decision and a minimum of 4 subjects must complete the study (up to Day 14) before proceeding to the next higher dosing cohort.

Together they will make one of the following determinations:

1. To continue with the study as planned.
2. To continue with the study and add additional safety evaluations.
3. To continue with the study and repeat a cohort.

4. To continue with the study by adjusting to an intermediate dose between the current dose and the previous lower dose (i.e., add an additional cohort) or to repeat a cohort, if:
  - a. At least 1 subject has a SAE or visit to the emergency room deemed to be possibly study drug related (see [Section 11.1.8.4](#)).
  - b. At least 25% of subjects in a cohort experience a grade  $\geq 2$  AE deemed to be possibly related to the study drug.
5. To stop the study. The study will be terminated if the following number of subjects meet any of the following criteria and the subjects were determined to have received active drug after unblinding:
  - I.  $\geq 1$  subject that receive drug in a cohort experience:
    - a. Life-threatening hypersensitivity reactions (e.g., anaphylaxis, respiratory symptoms, hypotension etc.).
    - b. Any grade thromboembolic event possibly related to the study drug.
    - c. Any grade bleeding possibly related to the study drug.
    - d. Presence of antibodies against human thrombin or prothrombin.
    - e. Presence of ADA.
  - II.  $\geq 2$  subjects that receive drug in a cohort:
    - a. Has a drug possibly or probably related SAE (see [Section 11.1.8.4](#)).
    - b. Experiences a drug related grade  $\geq 3$  toxicity (see [Section 11.1.8.3](#)).

Cohorts will be staggered to allow sufficient time for adequate review of safety and tolerability from the prior cohort.

Safety aPTT, PT, and thrombin time data from a cohort will be needed for a dose escalation decision. If aPTT and thrombin time are elevated at Day 14, a mixing study will be performed. If the mixing study does not normalize the aPTT and/or thrombin time, dose escalation will be postponed until ADA data is available. If either ADA assay are confirmed to be positive, the study will be stopped according to the dose escalation and stopping rules outlined above. APC-PCI complex level data will not be needed for a dose escalation decision.

When applicable, a written statement fully documenting the reasons for study termination will be provided to the IRB.

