#### **11.1.8 Adverse Events**

##### **11.1.8.1 Adverse Event Definition**

An AE means any untoward medical occurrence associated with the use of a drug in humans, whether or not considered drug related.

A suspected adverse reaction means any AE for which there is a reasonable possibility that the drug caused the AE. Reasonable possibility means there is evidence to suggest a causal relationship between the drug and the AE.

An AE can therefore be any unfavorable and unintended sign (including an abnormal laboratory finding), symptom, or disease temporally associated with the use of a medicinal (investigational) product, whether or not related to the medicinal (investigational) product [7].

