### 11.1.8.3 Reporting

All AEs that occurred during this clinical trial will be recorded. AEs will be coded using the most current version of MedDRA® available at Celerion.

The PI or designee will review each event and assess its relationship to drug treatment (unrelated, unlikely, possibly, probably, or likely,). Each sign or symptom reported will be graded on the FDA (Center for Biologics Evaluation and Research) toxicity grading scale for healthy volunteers 4-point severity scale (Grade 1, 2, 3 and 4) [8]. The date and time of onset, time relationship to drug dosing, duration, and outcome of each event will be noted.

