#### Relationship of AE:

The relationship of each AE to the study drug will be assessed using the following definitions:

Unrelated	

▪ The adverse event must clearly be caused by the participants clinical state, or the study procedure/conditions

▪ Definitely not related to drug

▪ Temporal sequence of an adverse event onset relative to administration of drug not reasonable

▪ Another obvious cause of an adverse event

Unlikely	

▪ Time sequence is unreasonable

▪ There is another more likely cause for an adverse event

Possibly	

▪ Corresponds to what is known about the drug

▪ Time sequence is reasonable

▪ Could have been due to another equally, likely cause

Probably	

▪ Is a known effect of the drug

▪ Time sequence from taking drug is reasonable

▪ Ceases on stopping the drug

▪ Cannot be reasonably explained by the known characteristics of the participants clinical state

Likely	

▪ Is a known effect of the drug (e.g. listed in IB)

▪ Time sequence from taking drug is reasonable

▪ Event stops upon stopping drug, event returns upon restarting drug

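### The relatedness terms in the escalation and stopping rules do not match the protocol's five-category causality scale, so on a literal reading the most strongly attributed events fall outside several triggers

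*Protocol*

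**What the plan says.** **The scale.** Protocol 11.1.8.3 asks the investigator to "assess its relationship to drug treatment (unrelated, unlikely, possibly, probably, or likely"). The table under Relationship of AE then gives bullets for each category, introduced by "The relationship of each AE to the study drug will be assessed using the following definitions". It does not say whether every bullet of a category must be met.

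- *Possibly* includes "Corresponds to what is known about the drug", reasonable timing, and an equally plausible other cause.
- *Probably* includes a known effect and "Ceases on stopping the drug".
- *Likely* includes "Is a known effect of the drug (e.g. listed in IB") and "Event stops upon stopping drug, event returns upon restarting drug".

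**The rules.** Section 10.4.1.4 uses three different expressions for relatedness. Rules 4a and 4b (intermediate dose or repeated cohort) and rules 5.I.b and 5.I.c (stop after one subject with a thromboembolic or bleeding event) name *possibly* alone. Rule 5.II.a (stop after two subjects) reads "Has a drug possibly or probably related SAE". Rule 5.II.b speaks of drug-related toxicity of grade 3 or higher and refers to 11.1.8.3, which sets no cut-off.

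**The design.** Under Protocol 10.1 each subject receives one bolus and joins one cohort. The Synopsis gives the push as 15 seconds to 1 minute.

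**The SAP.** Section 8.3 summarizes TEAEs by relationship. The shell of Table 14.3.1.3 has five relationship columns and no related / not related grouping.

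**The concern.** A rule that decides whether a first-in-human study stops should point to categories that the investigator can record, and should say which of them count. Here the same numbered list uses one category in some rules, two in another and an undefined term in a third. Rule 5.II.a writes out two categories, which makes it harder to assume that *possibly* alone elsewhere means *possibly* or stronger.

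Taken at face value, a bleeding event graded *probably* would not meet rule 5.I.c, while one graded *possibly* would. An SAE graded *likely* would not count towards rule 5.II.a, while a weaker attribution would. A second problem is that parts of the upper definitions depend on stopping or restarting a drug that is given once.

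**Working it through.** No stated sample size, power or error rate is involved, so there is no plan figure to reproduce. The check is a comparison of texts, followed by one illustration of scale.

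**Step 1: which categories each rule names (Protocol 10.4.1.4 against 11.1.8.3).**

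| Rule | Subjects needed | Named | Not named |
|---|---|---|---|
| 4a SAE or emergency-room visit | 1 | possibly | probably, likely |
| 4b grade 2 or higher AE | 25% of cohort | possibly | probably, likely |
| 5.I.b thromboembolic event | 1 | possibly | probably, likely |
| 5.I.c bleeding | 1 | possibly | probably, likely |
| 5.II.a SAE | 2 | possibly, probably | likely |
| 5.II.b grade 3 or higher toxicity | 2 | none (drug-related) | not mapped |

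Five of these six triggers omit at least one upper category, and the sixth has no mapping. Rules 5.I.a, 5.I.d and 5.I.e need no causality grade and are unaffected.

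**Step 2: can *possibly* be read as including the stronger grades?** Nothing in either document says so. One bullet for *possibly* is an equally plausible other cause, while one for *probably* is that the subject's clinical state does not explain the event. That reads as separate grades, and the SAP gives each its own column.

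**Step 3: do the definitions fit one bolus?**

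- *Likely*: return on restarting cannot be observed, because there is no second dose. If all bullets are required, *likely* cannot be assigned.
- *Probably*: ceasing on stopping fits poorly, since after a push of at most 1 minute there is no treatment left to stop. It is not impossible: Protocol 8.2.4 describes a transient, dose-dependent aPTT rise, and a known effect that resolves after the bolus could be read as meeting it.
- *Possibly*: no stopping or restarting element, so it can be used after one dose.

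**Step 4: scale of the omission in rule 5.II.a, taken alone.** The number of active subjects per cohort is 4 (Protocol 12.1.1). Two inputs are assumptions that the documents do not give: p, the chance that an active subject has an SAE graded *possibly*, *probably* or *likely*; and q, the share of those graded *likely*. With subjects independent and r = p(1 − q):

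P(rule met) = 1 − (1 − r)^4 − 4r(1 − r)^3

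For p = 0.3 with all three categories counted, r = 0.3 and 1 − 0.2401 − 0.4116 = 0.348. For q = 0.25, r = 0.225 and the result is 0.220.

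| p | *likely* counted, or q = 0 | as written, q = 0.25 | as written, q = 0.5 |
|---|---|---|---|
| 0.1 | 0.052 | 0.031 | 0.014 |
| 0.2 | 0.181 | 0.110 | 0.052 |
| 0.3 | 0.348 | 0.220 | 0.110 |
| 0.5 | 0.688 | 0.481 | 0.262 |

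For the single-subject rules 5.I.b and 5.I.c no calculation is needed: on a literal reading, one event graded *probably* or *likely* does not trigger them.

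**The case against.** The strongest reply is that the two parts of the point work against each other. If *likely* cannot be assigned because it needs a restart, leaving it out of rule 5.II.a loses nothing; this is the q = 0 column. That is correct for this one omission. It does not cover *probably*, which four other rules leave out. It also holds only if every bullet is required, which the protocol does not say. If the bullets are indicators rather than a joint test, *likely* can be assigned and then falls outside rule 5.II.a. The *Likely* column in the SAP shell leaves room for that.

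A second reply is that most readers would take *possibly* to mean at least possibly, and that other safeguards exist. The principal investigator reviews safety data before each escalation, the Safety Review Committee meets if findings are of concern, and Protocol 13.2 allows termination at any time. Rule 5.II.b could also catch a severe SAE graded *likely*, depending on how its undefined term is read. This lowers the practical risk, but it relies on judgement where the protocol sets out explicit triggers.

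A reader might go further and infer four things that the documents do not support:

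- That relatedness cannot be graded at all. *Possibly* can be assigned after one dose, and five of the rules name it.
- That *probably* is unattainable. The transient aPTT rise shows it is not ruled out.
- That a thromboembolic event could not be graded *possibly* for an antithrombotic. This is a pharmacological inference; no text requires a lower grade, and rule 5.I.b itself foresees the event. Protocol 11.1.8.1 also says "A suspected adverse reaction means any AE for which there is a reasonable possibility that the drug caused the AE", although it does not link that test to the five categories.
- That the upper relationship columns of Table 14.3.1.3 will be almost empty or misleading. No figure supports this, and the AE listing shows relationship event by event.

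**Conclusion.** The point holds as an internal inconsistency in rules that decide escalation and stopping. Rule 5.II.a omits one upper category, rules 4a, 4b, 5.I.b and 5.I.c omit two, and rule 5.II.b is not mapped to the scale. Followed literally, several triggers leave out the events with the strongest attribution. In addition, one element of *likely* cannot be observed in this design, and one element of *probably* fits it poorly.

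The conclusion rests on a literal reading of *possibly*, which the documents neither confirm nor exclude, and on *likely* being the strongest grade, which its place in the list and its restart element suggest. The practical size is moderate and cannot be estimated from the documents. The probabilities above depend on assumed p and q, and run from no loss at q = 0 to a fall from 0.348 to 0.110 at p = 0.3 and q = 0.5.

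**What to change.** Reconcile Protocol 10.4.1.4 with 11.1.8.3 and its Relationship of AE table:

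1. For each rule that uses relatedness, state which of the five categories count.
2. Define drug-related in rule 5.II.b in terms of the same categories.
3. State whether all bullets of a category must be met.
4. Reword the elements that depend on stopping or restarting drug so that they can be applied after a single dose.
5. Carry the same related / not related grouping into SAP Table 14.3.1.3.

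Which categories should trigger which rule is for the sponsor to decide; the request is that the sections agree. The cost is protocol wording, a CRF completion note and a grouping in one SAP table. No assessment, sample or subject is added.

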	
Blood samples will be collected for PD assessment (i.e., APC-PCI) of E-WE thrombin at scheduled time points listed in the Study Events Flow Chart (Section 6) predose and for 24 hours postdose.
 
Dose escalation to the next dose level (i.e., next cohort) will not take place until after the Principal Investigator (PI) has reviewed the safety data and informed the Sponsor of the findings. If any findings in the safety data are of concern, then the Safety Review Committee (SRC) comprised of but not limited to, the Sponsor, medical monitor, and the PI will convene to determine if adequate safety and tolerability from the previous cohorts, including activated partial thromboplastin time (aPTT), has been demonstrated to permit proceeding to the next cohort.
 
For each cohort, 14 days of safety data will be used and reviewed for a dose escalation decision. Data from all subjects in the appropriate cohort will be used and reviewed for a dose escalation decision. aPTT and thrombin time should be in the normal range (unless it is still within <math>\pm 10\%</math> of individual's baseline value taken at check-in) at Day 14 to rule out early cross-reacting antibodies to thrombin/prothrombin. A minimum of 4 subjects in each cohort must complete the study (up to Day 14) before proceeding to the next higher dosing cohort.
 
Subjects dosed on the same day will be dosed with an interval of at least 1 hour between subjects.
 
Subjects (including those who terminate early) will return on Days 14 and 28 for follow-up procedures (coagulation sample collection, thrombin time measurement, and immunogenicity sample collection) and to determine if any AE has occurred since the last study visit. If thrombin time and/or aPTT are found to be elevated beyond normal range (unless it is still within <math>\pm 10\%</math> of individual's baseline value at check-in) at Day 14, both tests will be repeated. If aPTT and/or thrombin time are elevated beyond normal range in the retest, a mixing study will be performed. The mixing study will be performed on Day 14 by mixing the subjects' plasma 1:1 with normal human pooled plasma. aPTT and thrombin time will be evaluated. If the aPTT and/or thrombin time does not correct to normal range, the presence of anti-drug antibodies (ADA) and cross-reacting prothrombin/thrombin antibodies will be presumed, and will be directly assessed before dose escalation decision.
 
Subjects who terminate the study early will be asked to continue aPTT and thrombin time monitoring as scheduled until Day 28.
 
Any subjects for whom aPTT and/or thrombin time did not reach

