- j If thrombin time and/or aPTT are found to be elevated at Day 14, both tests will be repeated. If aPTT and/or thrombin time are elevated beyond the normal range (unless it is still within  $\pm 10\%$  of individual's baseline value at check-in) in the retest, a mixing study will be performed. The mixing study will be performed on Day 14 by mixing the subjects' plasma 1:1 with normal human pooled plasma. aPTT and thrombin time will be evaluated. If the aPTT and/or thrombin time do not correct to normal range, the presence of ADA cross-reacting prothrombin/thrombin antibodies will be presumed. The applicable subject will remain at the CRU until

these test results are obtained. Subjects for whom aPTT and/or thrombin time did not reach  $\pm 10\%$  of the baseline value or within the normal range by Day 14, will return every 7 days ( $\pm 2$  days) until aPTT and thrombin time reach  $\pm 10\%$  of the baseline value or within the normal range.

- k Subjects in the sentinel group (Cohort 1 only) will be dosed at least 28 days prior to remaining subjects. The remaining subjects in Cohort 1 and subjects in the Cohorts 2, 3, and 4 will be dosed in two groups separated by at least 14 days. Dosing in each group will be staggered by at least 1 hour.
- l: Immunogenicity testing for ADA will be first performed on blood samples taken on Days 14 and 28. If ADA are found, the check-in sample of ADA will be evaluated.

Abbreviations: ADA = Anti-drug antibodies, AE = Adverse event, APC-PCI = Activated protein C with protein C inhibitor, aPTT = Activated partial thromboplastin time, C-I = Check-in, Chem = Chemistry, CRU = Clinical research unit, FSH = Follicle-stimulating hormone, FU = Follow-up, Hem = Hematology, HIV = Human immunodeficiency virus, INR = International normalized ratio, PD = Pharmacodynamic, PI = Principal Investigator, PT = Prothrombin time, Scr = Screening, UA = Urinalysis.

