### **10.2.4 Follow-up Visits (Day 14 and 28)**

Subjects (including those who terminate early) will return on Days 14 and 28 for follow-up procedures (coagulation sample collection, thrombin time measurement, and immunogenicity sample collection) and to determine if any AE has occurred since the last study visit. If thrombin time and/or aPTT are found to be elevated beyond normal range (unless it is still within  $\pm 10\%$  of individual's baseline value at check-in) at Day 14, both tests will be repeated. If aPTT and/or thrombin time are elevated beyond the normal range in the retest, a mixing study will be performed. The mixing study will be performed on Day 14 by mixing the subjects' plasma 1:1 with normal human pooled plasma and thrombin time evaluated. If the thrombin time does not correct, the presence of ADA and cross-reacting prothrombin/thrombin antibodies will be presumed and will be directly assessed before dose escalation decision. The applicable subject will remain at the CRU until these test results are obtained.

Subjects who terminate the study early will be asked to continue aPTT and thrombin time monitoring as scheduled until Day 28.

Any subjects for whom aPTT and/or thrombin time did not reach  $\pm 10\%$  of the baseline value or within the normal range by Day 14, will return every 7 days ( $\pm 2$  days) until aPTT and thrombin time reach  $\pm 10\%$  of the baseline value or within the normal range and for a FU visit (i.e., follow-up procedures and AE evaluation listed on Day 28 will be repeated) 7 days ( $\pm 2$  days) after it was reached.

Should any subjects withdraw or be withdrawn from the study, all the early termination evaluations should be performed if possible, including samples for PD assessments if applicable.

Immunogenicity samples will be collected at the follow-up visits. The follow-up procedures are listed in the Study Events Flow Chart [Section 6](#).

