#### **10.4.1.2 Planned Dose Levels**

The planned dose levels are as follows:

Cohort 1: 0.5 mcg/kg E-WE thrombin or matching placebo (IV bolus)

Cohort 2: 1.0 mcg/kg E-WE thrombin or matching placebo (IV bolus)

Cohort 3: 2.0 mcg/kg E-WE thrombin or matching placebo (IV bolus)

Cohort 4: 4.0 mcg/kg E-WE thrombin or matching placebo (IV bolus)

Note: The planned dose levels described above may be revised up or down or a dose level may be repeated based upon data from a previous dose level, however, doses will not exceed 4.0 mcg/kg without a protocol amendment.

For Cohort 1 there will be a sentinel group comprised of 2 subjects dosed at least 28 days before the remaining group of subjects; subjects will be randomized in a 1:1 ratio to active and placebo. The remaining subjects in the cohort will be dosed after evaluation of the sentinel subjects' Day 28 safety data and will be dosed in 2 groups separated by at least 14 days (2 subjects in the first group and 2 subjects in the second group). The placebo will be randomized to either group.

The Cohorts 2, 3, and 4 will be dosed in 2 groups separated by at least 14 days (2 subjects in the first group and 3 subjects in the second group). The placebo will be randomized to either group.

Thrombin time and aPTT at Day 14 will be tested to evaluate whether or not subjects may be generating neutralizing antibodies to thrombin/prothrombin. If the thrombin time and aPTTs are normal, the next cohort may be dosed if the rest of the safety data is deemed acceptable by the PI or SRC, as applicable. Confirmation of safety data from the previous cohorts will include for Cohort 1, 6 subjects (4 active and 2 placebo) and for Cohorts 2, 3, and 4, 5 subjects (4 active and 1 placebo).

If thrombin time and/or aPTT are found to be elevated beyond normal range (unless it is still within  $\pm 10\%$  of individual's baseline value at check-in) at Day 14, both tests will be repeated. If aPTT and/or thrombin time are elevated beyond normal range in the retest, a mixing study will be performed. The mixing study will be performed by mixing the subjects' plasma 1:1 with normal human pooled plasma. aPTT and thrombin time will be evaluated. If the aPTT and/or thrombin time do not correct to normal range, the presence of ADA and cross-reacting prothrombin/thrombin antibodies will be presumed, and will be directly assessed before a dose escalation decision.

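### The Day 14 mixing-study rule that brings antibody data forward before dose escalation differs between protocol sections in trigger, read-out and sample-shipment condition

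*Protocol*

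**What the plan says.** Five places in the protocol state the mixing-study rule, and a sixth controls when antibody samples are sent.

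- **Synopsis, Study Design.** If either test is above normal at Day 14 and not within 10% of baseline, both are repeated. If either is above normal on repeat, a mixing study follows and both tests are read on the mix. "If the aPTT and/or thrombin time does not correct to normal range", antibodies are presumed and assayed before the escalation decision. Separately, at Day 14 "aPTT and thrombin time should be in the normal range", with the 10% allowance.
- **Flow Chart, footnote j.** The trigger is again either test on repeat, but the 10% allowance is attached to the repeat. The read-out is "If the aPTT and/or thrombin time do not correct to normal range, the presence of ADA cross-reacting prothrombin/thrombin antibodies will be presumed". The footnote does not mention the escalation decision.
- **Section 10.2.4.** Trigger and allowance are as in the Synopsis, but only the thrombin time is evaluated on the mix: "If the thrombin time does not correct, the presence of ADA and cross-reacting prothrombin/thrombin antibodies will be presumed".
- **Section 10.4.1.2.** "If aPTT and/or thrombin time are elevated beyond normal range in the retest, a mixing study will be performed". Both tests are read, failure of either counts, and antibodies are assayed before the escalation decision. This section also makes dosing of the next cohort conditional on both tests being normal and the remaining safety data being acceptable.
- **Section 10.4.1.4.** "If aPTT and thrombin time are elevated at Day 14, a mixing study will be performed". Neither a repeat test nor the 10% allowance appears. The next sentence postpones escalation until antibody data are available if the mix fails to normalise either test.
- **Section 11.1.7.1.** Antibody samples go to the laboratory at the end of the study unless antibodies are suspected because the thrombin time is raised at Day 14 or Day 28.

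The SAP does not describe the mixing study, so it cannot settle the question.

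**The concern.** Section 10.4.1.4 ends the study if one subject on active drug in a cohort has anti-drug antibodies or antibodies to human thrombin or prothrombin. Antibody results are not routinely available when escalation is decided. Samples normally wait until the end of the study, and the list of data that the Safety Review Committee must review omits immunogenicity. The mixing study is the protocol's stated route for bringing antibody data forward before the next cohort.

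That route depends on which section is followed. Section 10.1 refers the escalation decision to Section 10.4.1.4, so the differing trigger cannot be set aside as secondary text. Section 10.4.1.2 says both tests are run to look for antibodies, so a signal in only one of them should be handled the same way throughout. If it is not, a termination criterion that one subject can meet may be unassessed when the dose is doubled.

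**Working it through.** There is no stated figure to reproduce, because the sample size was set without statistical considerations (Section 12.1.1). The check applies each rule, as written, to the possible abnormal patterns.

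**Step 1: notation.** Let A = 1 if the aPTT is elevated (on repeat, where a repeat is specified) and stays long on mixing. Let T = 1 for the same in thrombin time. A rule raises the antibody presumption or hold only if its trigger and its read-out are both met.

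| Place | Trigger | Read-out | aPTT only (A=1, T=0) | Thrombin time only (A=0, T=1) | Both (A=1, T=1) |
|---|---|---|---|---|---|
| Synopsis | A or T | A or T | presumed; assay before decision | presumed; assay before decision | presumed; assay before decision |
| Footnote j | A or T | A or T | presumed | presumed | presumed |
| 10.2.4 | A or T | T | mixed, not presumed | presumed; assay before decision | presumed; assay before decision |
| 10.4.1.2 | A or T | A or T | presumed; assay before decision | presumed; assay before decision | presumed; assay before decision |
| 10.4.1.4, literal | A and T | A or T | no mix | no mix | escalation postponed |

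**Step 2: counts.** The aPTT-only pattern is caught in 3 of 5 places, the thrombin-time-only pattern in 4 of 5, and both together in 5 of 5. With four cohorts the rule is applied at three planned escalations: 0.5 to 1.0, 1.0 to 2.0 and 2.0 to 4.0 mcg/kg, each a doubling.

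**Step 3: the 10% allowance.** It sits at the first test in the Synopsis, 10.2.4 and 10.4.1.2, at the repeat in footnote j, and nowhere in the rule in 10.4.1.4. Take one test at a time, with upper normal limit U and baseline B, and both readings above U. The two placements give different mixing decisions only if the readings fall on opposite sides of the allowance.

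- First reading outside, repeat within: mixing study in the Synopsis, 10.2.4 and 10.4.1.2, but not in footnote j.
- First reading within, repeat outside: footnote j repeats and mixes; the other three never repeat the test.

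Either case needs a reading above U but no more than 1.1 × B, so B > U/1.1 = 0.909 U. The baseline must lie within about 9% of the upper limit or above it. This is a narrow discrepancy.

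**Step 4: sample shipment.** An aPTT-only signal does not meet the stated condition for early shipment in 11.1.7.1, although the Synopsis and 10.4.1.2 require direct antibody assessment before the decision if that signal does not correct.

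**Step 5: how often it could arise (illustration only).** The documents give no frequency for isolated prolongation. Assume a per-subject probability p and independent subjects. The chance of at least one such subject in a cohort of n is 1 − (1 − p)^n.

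| Assumed p | n = 5 | n = 6 |
|---|---|---|
| 1% | 4.9% | 5.9% |
| 2.5% | 11.9% | 14.1% |
| 5% | 22.6% | 26.5% |
| 10% | 41.0% | 46.9% |

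These are chances that the sections would have to be reconciled in practice. They are not chances of a missed antibody.

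**The case against.** The strongest reply is that Section 10.4.1.4 says what happens when both tests are elevated. It does not say that a mix is made *only* then, or that an isolated prolongation may proceed. Its read-out sentence counts failure of either test, which suggests loose drafting and not a deliberate both-tests rule. The sections can also be followed together: mix when either test is elevated, read both, and nothing in the protocol is breached. Other safeguards exist. The Synopsis and Section 10.4.1.2 expect both tests to be normal before escalation, Section 10.4.1.4 requires coagulation data and investigator review every time, and the study has one centre.

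Much of this stands. A reader might infer that the protocol lets a subject with an isolated aPTT prolongation through to the next dose. The documents do not support that: not being caught by the mixing-study step is not the same as being cleared for escalation. Nor is the stricter handling confined to one section, since three places presume antibodies in this subject.

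The reply does not remove the conflict. Section 10.4.1.4 uses *and* in the trigger and *and/or* shortly afterwards, so a literal reading is reasonable. Even if that *and* is shorthand, Section 10.2.4 still judges an isolated aPTT prolongation on a thrombin time that was not abnormal, and Section 11.1.7.1 still ties early shipment to thrombin time. The remaining safeguards rely on judgement: the Safety Review Committee convenes only if a finding is of concern.

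**Conclusion.** The contradiction is in the current protocol text. Section 10.4.1.4 is the outlier on the trigger and the repeat test, Section 10.2.4 is the outlier on the read-out, and footnote j differs on where the allowance sits. Section 11.1.7.1 has a shipment condition that matches only the thrombin time read-out.

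The consequence is limited to single-test abnormalities, apart from the narrow allowance cases and one further pattern: if both tests are elevated and only the aPTT stays long on the mix, Section 10.2.4 alone would not presume antibodies. Where both are elevated on repeat, outside the allowance, and neither corrects, all five statements of the rule lead to an antibody presumption or a hold.

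The conclusion rests on reading each section as written. It shows that the rule does not determine one action for the same subject. It does not show that such a subject would be missed, and no frequency can be attached from the documents. Because the rule stands before every dose doubling and feeds a one-subject termination criterion, it should be settled before the first escalation decision.

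**What to change.** Reconcile the Synopsis, Flow Chart footnote j and Sections 10.2.4, 10.4.1.2, 10.4.1.4 and 11.1.7.1 to a single algorithm that fixes:

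1. which test or tests trigger the mixing study;
2. whether a repeat test comes first;
3. whether the 10% allowance applies to the first test, the repeat or both;
4. which test or tests are read on the mix, and what counts as failure to correct;
5. a condition for early shipment of antibody samples that matches items 1 and 4.

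State it once in Section 10.4.1.4 and have the other places refer to it. Which clinical rule applies is for the sponsor and investigator to decide; this review does not choose between them.

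The change is to protocol wording, through an amendment approved under Section 13.8. Both tests are already scheduled at Day 14. The number of mixing studies and early shipments may change with the rule chosen.
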